3.4 Conventions

Continuous variables will be summarized with descriptive statistics (mean, standard deviation, median, quartiles, minimum, and maximum). Standard deviation can be replaced by standard error for special requirement. Categorical variables will be summarized using frequencies and percentages.

In efficacy analysis, month is calculated by cycle (28 days). For the analysis other than efficacy, the following rules will be used for the days to months/years conversion:

- 1 month = 30.4375 days;
- 1 year = 365.25 days.

All data collected on the CRF will be presented in data listings upon request by the Regulatory agency. All statistical analyses will be performed using SAS® version 9.2 or higher.

4. Subject Information

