A recently published single institution study developed a new approach for evaluating clinical trial endpoints for testing therapies for second-line treatment of cGVHD (Inamoto 2013). The primary study endpoint was failure free survival (FFS) defined as the absence of a third line therapy, NRM, and recurrent malignancy. This was a retrospective study of 312 patients at the Fred Hutchinson Cancer Research Center who had received systemic steroids for the treatment of cGVHD at a dose of at least 0.5 mg/kg/day before second line treatment, were on systemic immunosuppressive therapy when the second line therapy was initiated, and had received second line therapy due to cGVHD progression after at least one week of initial therapy or due to lack of improvement after at least two weeks of initial therapy. FFS was reported at 56% at 6 months and at 45% at 12 months from the start of second line therapy (Inamoto 2013). With 48 months of follow-up, only 15% of patients were able to successfully withdraw from all immunosuppressive therapy. The major cause of FFS was treatment change (ie, need for third line therapy) and the study results have set a benchmark for second line cGVHD therapy (Inamoto 2013).

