1.1.3 Exploratory Objectives

The exploratory objective covered by this analysis plan is:

- To evaluate the clinical efficacy of ibrutinib by measuring failure free survival at 6 and 12 months

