5.2.1 Rate of Sustained Response

Sustained response is defined as NIH-defined response that sustain continuously for at least 5 months (140 days). Considering 3 days visit window allowed by protocol, the bound of sustained response is defined as 137 days. Intermittent SD assessment between response assessments is allowed. Of the total number of subjects who responded to study treatment, the proportion of subjects who meet the sustained response criterion will be summarized in the same manner as the primary endpoint. If the lower bound of the CI of the response rate is $\geq 25\%$, this secondary objective is achieved.

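### The SAP counts an efficacy month as 28 days and any other month as 30.4375 days, so DOR in months reads 8.7% longer and, by implication, 6- and 12-month FFS is read about 15 and 29 days early

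*SAP*

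**What the plan says.** SAP 3.4 sets two month lengths. For efficacy: "In efficacy analysis, month is calculated by cycle (28 days". For the rest: "For the analysis other than efficacy, the following rules will be used for the days to months/years conversion", namely "1 month = 30.4375 days" and "1 year = 365.25 days".

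The efficacy rule is used once explicitly. SAP 5.2.1 requires a response lasting "for at least 5 months (140 days", then lowers the bound to 137 days for the 3-day visit window.

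DOR (SAP 5.2.2) and FFS (SAP 5.3) both belong to SAP section 5, Efficacy Analysis. Each is summarised by a Kaplan-Meier median and curve, and neither section names a time unit or a landmark day. The FFS objective in SAP 1.1.3 is "To evaluate the clinical efficacy of ibrutinib by measuring failure free survival at 6 and 12 months".

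Protocol 1.5 describes a retrospective single-institution cohort on second-line therapy: "FFS was reported at 56% at 6 months and at 45% at 12 months from the start of second line therapy". It calls those results a benchmark. Protocol 7.2.3 refers to the same study for how FFS with corticosteroid requirements at 6 and 12 months will be assessed.

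**The concern.** The same number of days turns into more months in an efficacy table than in any other table. A reader who sets median DOR beside time on study, or beside a DOR from another trial in calendar months, would be comparing different units.

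For FFS the consequence goes beyond a label. The month length decides where on the curve the 6- and 12-month values are read. An FFS curve never rises, so reading it earlier can only raise the estimate or leave it unchanged. The direction therefore always favours the drug, whatever the size.

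**Working it through.** **Inputs.** Month lengths of 28 and 30.4375 days (SAP 3.4); 140 and 137 days (SAP 5.2.1); FFS at 6 and 12 months (SAP 1.1.3); 56% and 45% (Protocol 1.5); about 40 subjects at the recommended Phase 2 dose (SAP 1.4). Days below are elapsed days.

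**1. The plan's own figure.** 5 × 28 = 140 days, as SAP 5.2.1 states. With the other month, 5 × 30.4375 = 152.2 days. So the 28-day rule is the one in use. In months of 30.4375 days, 140 days is 140/30.4375 = 4.60 and 137 days is 137/30.4375 = 4.50.

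**2. DOR.** The ratio is 30.4375/28 = 1.087, or 8.7% longer. For 280 days: 280/28 = 10.0 months against 280/30.4375 = 9.2.

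An example of DOR exceeding time on study: a response is first documented at Week 5 (Day 29) and progression at Day 730, which is also the last day on study.
- DOR = 730 − 29 = 701 days; 701/28 = 25.0 months.
- Time on study = 730 days; 730/30.4375 = 24.0 months.

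The response began four weeks into the study, yet it appears a month longer than the study.

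**3. FFS reading times.**

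| Landmark | 28-day month | 30.4375-day month | Early by |
|---|---|---|---|
| 6 months | 168 days | 182.6 days | 14.6 days |
| 12 months | 336 days | 365.25 days | 29.25 days |

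**4. Size of the FFS shift.** Assume that FFS follows the quoted 56% and 45% and that those are in calendar months. The curve between these points is not in the documents, so simple shapes give a range.

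At 6 months:
- Constant hazard from 0 to 6 months: 0.56^(168/182.625) = 58.7%, or +2.7 points.
- Straight line: 1 − 0.44 × 168/182.625 = 59.5%, or +3.5 points.
- Hazard just before 6 months already down to the 6-to-12-month rate: 0.56 × (0.56/0.45)^(14.625/182.625) = 57.0%, or +1.0 point.

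At 12 months:
- Constant hazard from 6 to 12 months: 0.56 × (0.45/0.56)^((336 − 182.625)/182.625) = 46.6%, or +1.6 points.
- Straight line: 0.56 − 0.11 × (336 − 182.625)/182.625 = 46.8%, or +1.8 points.

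**5. Set against precision.** For 40 subjects and FFS of 56%, ignoring censoring, the 95% half-width is 1.96 × √(0.56 × 0.44/40) = 0.154, about 15 points.

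**The case against.** The convention is open and applied consistently. SAP 5.2.1 prints the day count beside the month count, so nobody is misled about the sustained-response bound. A 28-day unit also fits the design: visits run every 4 weeks to Week 25 and every 12 weeks from then on, and SAP Appendix 8.1 lists its windows under a cycle heading with targets at Days 169 and 337, which are 168 and 336 days after Day 1. SAP 3.3 bases time-to-event endpoints on study day, so no event date and no curve shape changes. The SAP does not say that DOR will be reported in months, and SAP 5.3 does not write out any FFS landmark.

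Most of this stands. It rules out calling the convention an error or a concealed one, and the landmark days are an inference from the objective and the month rule together. What does not stand is the visit grid as a reason for FFS. Its events are death, relapse and start of new therapy (SAP 5.3), each with its own date, so a calendar reading is available.

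A reader might also infer that FFS is to be compared with the published cohort and that the early reading biases that comparison. The documents do not support this. The benchmark wording is background, Protocol 7.2.3 is a reference for method, FFS is exploratory and descriptive (Protocol 10.4), and no test or threshold uses 56% or 45%. The cohort had second-line therapy, whereas this trial admits subjects with up to three previous treatments (Protocol 4.1), so even an informal comparison would be loose.

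**Conclusion.** The point holds as one of units and reporting. Any DOR given in months under SAP 3.4 is 8.7% longer than the same days in a non-efficacy table. That follows from the plan's two constants alone.

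For FFS, the rule implies readings about 15 and 29 days before calendar 6 and 12 months. The resulting shift of about +1 to +3.5 points at 6 months and under +2 at 12 rests on three assumptions: that the landmarks follow the 28-day rule, that the quoted cohort figures are in calendar months, and that FFS here resembles them with one of the simple shapes above. It is small beside a half-width of about 15 points, but its direction is fixed.

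Two wider readings should be resisted. One is that all efficacy results are overstated: the primary response rate and its success rule involve no month, corticosteroid dose is averaged by week, and symptom scores are tied to visit windows defined in days. The other is that the 140-day bound is wrong because five calendar months are 152 days. The SAP defines the bound in days, and the protocol's five-month endpoint (Protocol 10.2.2.1) carries no day count to contradict it.

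**What to change.** - **SAP 3.4:** use 30.4375 days per month for DOR and FFS, as for the non-efficacy analyses.
- **SAP 5.3:** state the FFS landmarks as days 183 and 365. If days 168 and 336 are preferred, label them 24 and 48 weeks.
- **SAP 5.2.1:** leave the sustained-response bound at 140 days (137 with the window) and keep the protocol's endpoint name. Report the day count with it, since 140 days is 4.6 calendar months.

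This needs SAP wording only and no new data. The downside is that DOR in months becomes about 8% shorter (28/30.4375 = 0.920) and the FFS estimates may be slightly lower.

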4.1 Subject Enrollment

Subject enrollment will be summarized by study center as based on all enrolled subjects.

4.2 Subject Disposition

The information will be summarized as follows for subject disposition:

- Subject status for the study
- Reason for study termination for subjects who were off the study
- Time on study
- Subject status for the study drug
- Reason for study treatment discontinuation for subjects who discontinued study drugs

4.3 Important Protocol Deviations

In general, protocol violations/deviations will be reviewed by the study team during the study, and important protocol deviations will be determined based on the review. The information of important protocol deviations will be generated based on the review outcome for all subjects.

4.4 Demographics and Baseline Characteristics

All demographic and baseline characteristics will be summarized for the all treated population.

The demographics include:

- Age
- Gender, race, and ethnicity

The baseline characteristics include:

- Weight and height
- Estimated creatinine clearance rate (eCcr)
- Estimated creatinine clearance rate groups (< 30 mL/min; 30 – < 60 mL/min, >= 60 mL/min)
- Baseline hemoglobin and platelets

4.5 Baseline Disease Characteristics and Baseline Medications

The history information related to the disease will be summarized. The key baseline characteristics include:

- Months from Last Transplantation to Enrollment, which is defined as the time period between the last transplantation and enrollment
- Months from Initial cGVHD Diagnosis Date, which is defined as the time period between the initial cGVHD diagnosis and enrollment
- Months from Transplantation to initial cGVHD diagnosis date
- Karnofsky performance status score at baseline
- Number of prior cGVHD treatment regimens
- Organs involved in cGVHD

4.6 Concomitant Medications

Reported medications will be coded to a generic name and an Anatomical Therapeutic Chemical (ATC) class according to World Health Organization (WHO) Drug dictionary and will be summarized.

Medication that was taken before the first dose of the study drug is called prior medication. Concomitant medications are defined as medications that were taken between the date of the first dose of study drug and the date of the last dose of study drug.

Concomitant medications will be summarized by therapeutic class and preferred term. The summary of usage of CYP3A inhibitors as well CYP3A inducers will be provided separately.

The summary of usage of anticoagulants and antiplatelets will also be provided.

Subsequent cGVHD therapies taken after the start of study drug will be summarized separately.

4.7 Extent of Study drug Exposure

The exposure to study drugs will be summarized. The following parameters will be summarized when applicable:

- Duration of treatment
- Cumulative dose received on study
- Dose intensity
- Relative dose intensity
- Dose reduction due to AE
- Dose interruption with 7 days or more due to AE

5. Efficacy Analysis

Unless specified otherwise, all information from the Phase 1b and Phase 2 parts of the study will be combined for efficacy analysis. The primary population used to evaluate efficacy is All Treated Population and where applicable, the response evaluable analysis set will be used as a sensitivity analysis to assess the robustness of the results.

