5.3.1.4. Dose Modification for Adverse Reactions

During Phase 1b, ibrutinib will be stopped according to DLT rules in [Section 5.2.1](#) during the 28 day DLT window. Thereafter, subjects enrolled in Phase 1b will have ibrutinib modified or discontinued according to the guidelines in [Table 1](#).

For Phase 2, the dose of ibrutinib should be modified according to the dose modification guidelines in [Table 1](#) if any of the following toxicities occur:

- Grade 3 ANC (<1,000/ μ L) with an associated temperature $\geq 38.5^{\circ}\text{C}$
- Grade 4 ANC (<500/ μ L) for more than 7 days. Refer to [Section 6.1.1](#) for instruction regarding the use of growth factor support
- Grade 3 thrombocytopenia (<50,000/ μ L) in the presence of Grade ≥ 2 bleeding events
- Grade 4 thrombocytopenia (<25,000/ μ L)

- Grade 3 or 4 nausea, vomiting, or diarrhea if persistent, despite optimal anti-emetic and/or anti-diarrheal therapy
- Any other Grade 4 or unmanageable Grade 3 toxicity attributed to ibrutinib

Table 1: Ibrutinib Dose Modifications

Hematologic Adverse Events	
Occurrence	Action to be Taken
First	Withhold ibrutinib until recovery to an ANC ≥ 750 or platelets $> 25,000$ with no evidence of Grade ≥ 2 bleeding; may restart at original dose level
Second	Withhold ibrutinib until recovery to an ANC ≥ 750 or platelets $> 25,000$ with no evidence of Grade ≥ 2 bleeding; may restart at 1 dose level lower
Third	Withhold ibrutinib until recovery to an ANC ≥ 750 or platelets $> 25,000$ with no evidence of Grade ≥ 2 bleeding; may restart at 1 dose level lower
Fourth	Discontinue ibrutinib ^a
Non-Hematologic Adverse Events	
First	Withhold ibrutinib until recovery to Grade ≤ 1 or baseline; may restart at original dose level
Second	Withhold ibrutinib until recovery to Grade ≤ 1 or baseline; may restart at 1 dose level lower
Third	Withhold ibrutinib until recovery to Grade ≤ 1 or baseline; may restart at 1 dose level lower
Fourth	Discontinue ibrutinib ^a

^a. If ibrutinib is discontinued for toxicity, subject will end the Treatment Phase of the study.

For Grade 3 or 4 atrial fibrillation or persistent atrial fibrillation of any grade, consider the risks and benefits of ibrutinib treatment. If clinically indicated, the use of anticoagulants or antiplatelet agents may be considered for the thromboprophylaxis of atrial fibrillation ([Section 6.2.4](#)).

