6.2. Medications to be Used with Caution

6.2.1. CYP3A Inhibitors/Inducers

Ibrutinib is metabolized primarily by CYP3A. Avoid co-administration with strong CYP3A (eg, ketoconazole, indinavir, nelfinavir, ritonavir, saquinavir, clarithromycin, telithromycin, itraconazole, and nefazadone) or moderate CYP3A inhibitors and consider alternative agents with less CYP3A inhibition. If a strong CYP3A inhibitor must be used, reduce ibrutinib dose to 140 mg or withhold treatment temporarily for the duration of the inhibitor use. Subjects should be monitored for signs of ibrutinib toxicity. If a moderate CYP3A inhibitor must be used, reduce ibrutinib to 140 mg for the duration of the inhibitor use. No dose adjustment is required in combination with mild inhibitors. Avoid grapefruit and Seville oranges during ibrutinib treatment, as these contain moderate inhibitors of CYP3A (see [Section 5.3.1.2](#)).

Avoid concomitant use of strong CYP3A inducers (eg, carbamazepine, rifampin, phenytoin, and St. John's Wort). Consider alternative agents with less CYP3A induction.

A list of common CYP3A inhibitors or inducers is provided in [Appendix J](#); a comprehensive list of inhibitors, inducers, and substrates may be found at <http://medicine.iupui.edu/clinpharm/ddis/table.aspx>. This website is continually revised and should be checked frequently for updates.

For the most comprehensive effect of CYP3A inhibitors or inducers on ibrutinib exposure, please refer to the current version of the IB.

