10.5. Safety Analysis

The safety variables to be analyzed include adverse events, clinical laboratory test results (hematology and chemistry), and other safety measurements. They will be summarized by descriptive statistics. No formal statistical testing is planned.

Exposure to ibrutinib first dose and reasons for discontinuation from study treatment will be tabulated.

Adverse Events

Adverse event parameters to be evaluated are the type, incidence, and intensity of adverse events; the relationship of adverse events to ibrutinib; and the action taken with respect to ibrutinib treatment due to adverse events.

The verbatim terms used in the eCRF will be coded using the Medical Dictionary for Regulatory Activities (MedDRA).

Treatment-emergent adverse events are those adverse events occurring after the first dose of study drugs and within 30 days following the last dose of study drug; any adverse event that is considered study drug-related regardless of the start date of the event; or any adverse event that is present at baseline but worsens after the first administration of study drug in severity or is subsequently considered drug-related by the Investigator. All treatment-emergent adverse events will be included in the analysis.

For each adverse event, the percentage of subjects who experience at least 1 occurrence of the given event will be summarized. The number and percent of subjects with treatment-emergent adverse events will be summarized according to intensity (NCI CTCAE v. 4.03) and drug relationship as well as categorized by system organ class and preferred term. Summaries, listings, datasets, or subject narratives may be provided, as appropriate, for those subjects who die, who discontinue treatment due to an adverse event, or who experience a severe or a serious adverse event.

Clinical Laboratory Tests

All laboratory values will be converted to standard international units and will be graded using the [NCI CTCAE v. 4.03](#).

A summary of the shifts in selected laboratory hematology and serum chemistry parameters from baseline to the worst toxicity grade during the study will be tabulated.

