6.1 Adverse Events

The verbatim terms used in the CRF by investigators to identify adverse events (AEs) will be coded using the Medical Dictionary for Regulatory Activities (MedDRA). Adverse events will be graded by the investigator according the National Cancer Institute common terminology criteria for adverse events (CTCAE) Version 4.03.

Drug-related adverse events are those assessed by investigator as being possibly related or related to study drug.

Treatment-emergent AEs are defined as those events that 1) occur on or after the first day of study drug, and within 30 days following the last dose of study drug or initiation of subsequent cGVHD therapy; 2) any event with missing onset date and its resolution date is during the treatment phase unless the event was indicated in the CRF that was present

before the first day of study drug; 3) any event that is considered study drug-related regardless of the start date of the event; or 4) any event that is present at baseline but worsens in severity or is subsequently considered drug-related by the investigator.

For each adverse event, the percentage of subjects who experience at least 1 occurrence of the given event will be summarized. In the event a patient experiences repeat episodes of the same AE, then the event with the highest severity grade will be used for purposes of incidence tabulations.

Summaries of AEs include:

- Incidence of AEs and serious adverse events (SAEs) by System Organ Class (SOC) and preferred term
- Incidence of AEs and SAEs by preferred term
- Incidence of drug-related AEs and SAEs

AE leading to study treatment discontinuation for the subjects who discontinued study drug due to AE, AE leading to dose reduction, and AEs leading to death will be summarized.

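### SAP 4.7 and 6.1 leave AE-driven holds of 1 to 6 days, followed by restart at the same dose, out of every planned dose-modification count and AE-by-action table

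*SAP*

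**What the plan says.** SAP 4.7 (Extent of Study drug Exposure) lists two dose-modification items. One is "Dose reduction due to AE", with no limit on how long the reduction lasts. The other is "Dose interruption with 7 days or more due to AE". The SAP gives no reason for the 7-day cut.

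SAP 6.1 (Adverse Events) lists incidence summaries and then the summaries by consequence. These cover AEs leading to treatment discontinuation, and then "AE leading to dose reduction, and AEs leading to death will be summarized". Interruption is not named.

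Protocol 5.3.1.4, Table 1, sets the action by occurrence. For a first non-hematologic event it reads "Withhold ibrutinib until recovery to Grade ≤ 1 or baseline; may restart at original dose level". For a first hematologic event the hold lasts until counts recover, "with no evidence of Grade ≥ 2 bleeding; may restart at original dose level". A lower dose level appears only from the second occurrence. No minimum hold length is given.

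Protocol 10.5 (Safety Analysis) includes among the AE parameters to be evaluated "the action taken with respect to ibrutinib treatment due to adverse events". It sets no duration limit.

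**The concern.** Under Table 1 the first response to a dose-modifying toxicity is neither a reduction nor a discontinuation. It is a hold that may end with the same dose. The SAP plans a count and an AE table for reductions, and an AE table for discontinuations. For holds it plans a count only at 7 days or more, and no AE table at any length. The most common entry point to the dose-modification scheme is thus the one least covered by the reporting plan.

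Safety and tolerability is the primary objective of Phase 1b and a secondary objective of Phase 2. How often an AE forced the drug to be stopped, even briefly, is a direct description of tolerability. An interruption rate that silently excludes short holds would be read as lower than it was.

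**Working it through.** The plan states no figure on this point, so there is none to reproduce. The check is a comparison of text, followed by a short calculation of what dose intensity would show.

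**1. Following one event through the plan.** Take a subject in Phase 2, or in Phase 1b after day 28, with a first dose-modifying toxicity that recovers within 1 to 6 days and a restart at the same dose.

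- SAP 4.7, reduction due to AE: not counted, because the dose did not change.
- SAP 4.7, interruption: not counted, because the hold was shorter than 7 days. (This reads the 7 days as one episode; the SAP does not say.)
- SAP 6.1, AEs leading to discontinuation, reduction or death: not included.
- SAP 6.1, AE incidence: included, but without the fact that the drug was held.
- SAP 3.4, listings: available only if a regulatory agency asks.

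A hold of 7 days or more would be counted in SAP 4.7, but the AE that caused it would still be in no AE-by-action table.

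**2. Scope in Phase 1b.** Protocol 5.3.1.4 says that during the 28-day DLT window the drug is stopped under the DLT rules, and that Table 1 applies to Phase 1b subjects afterwards. The gap therefore excludes that window.

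**3. What dose intensity would show.** SAP 3.1.8 defines relative dose intensity as dose given divided by treatment duration times the assigned daily dose. SAP 3.1.4 counts duration from first to last dose, so held days stay in the denominator. With full dose on all other days, treatment duration T and hold length h:

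relative dose intensity = (T − h) / T

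T and h are assumptions, because the documents give neither.

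| T (days) | h = 3 | h = 6 |
|---|---|---|
| 28 | 25/28 = 89.3% | 22/28 = 78.6% |
| 84 | 81/84 = 96.4% | 78/84 = 92.9% |
| 168 | 165/168 = 98.2% | 162/168 = 96.4% |
| 365 | 362/365 = 99.2% | 359/365 = 98.4% |

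A short hold is visible over short exposure and faint over long exposure. In neither case is it tied to an AE. For comparison, a 7-day hold over 168 days gives 161/168 = 95.8%, which is 0.6 points below the 6-day hold. Yet the first is counted as an interruption and the second is not.

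**4. Whether the data exist.** Protocol 11.4.1 and 11.4.2 require the action taken to be recorded for each AE, and 5.3.1.4 requires dose changes to go in the Dose Administration eCRF. The 7-day rule itself cannot be applied without the dates and the reason for each hold.

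**The case against.** **The toxicities are not hidden.** A reader might infer that toxicities which forced a hold go unreported. The documents do not support that. SAP 6.1 tabulates AEs and SAEs by system organ class and preferred term, with drug-related events separately and repeat episodes at the highest grade. SAP 6.2 summarises the worst post-baseline laboratory grade. Only the link from event to short hold is lost. This objection stands and limits the point.

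**Dose intensity captures short holds.** It does, as the table shows, so one cannot say that it fails to reveal them. It does not attribute them to an AE.

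**The protocol commitment remains.** The first list in SAP 6.1 is introduced as what the summaries include, which need not be exhaustive. Protocol 10.5 also allows listings or narratives for severe or serious events. This stands in part: the SAP does not withdraw the commitment. But Protocol section 10 leaves the specific details to the SAP, and the SAP supplies them for reduction and discontinuation only.

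**The 7-day cut is a pre-specified descriptive choice.** That is correct. No interruption endpoint is defined that it contradicts.

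**Phase 1b decisions are untouched.** A reader might infer that DLT counts or the choice of Phase 2 dose are affected. They are not. The DLT rules govern the window, and the SAP's safety section leaves the DLT review to the Dose Level Review Meeting.

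**Inhibitor-driven reductions.** A reader might extend the criticism to reductions made for CYP3A inhibitors under Protocol 6.2.1, which SAP 4.7 does not count. That is a matter of preference. SAP 4.6 summarises CYP3A inhibitor use separately, limiting a tolerability count to AEs is reasonable, and no passage promises reductions by reason. Their effect on relative dose intensity also depends on whether the assigned daily dose in SAP 3.1.8 stays fixed, which the SAP does not say.

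**Conclusion.** The point holds as a narrow reporting gap. For Phase 2, and for Phase 1b after the DLT window, AE-driven holds of 1 to 6 days with restart at the same dose fall outside every planned dose-modification count and AE-by-action table. The SAP thereby carries out only part of what Protocol 10.5 sets out to evaluate.

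The number of holds missed cannot be estimated from the documents. It may be anything from none to all first-occurrence holds, depending on how quickly toxicities recover. The conclusion assumes that the 7 days refers to a single episode and that the summaries named in SAP 4.7 and 6.1 are those that will be produced. It bears on the description of tolerability and on no efficacy conclusion. The change is worth making because it is cheap, not because the analysis is invalid without it.

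**What to change.** In SAP 4.7, replace the interruption item with: *Dose interruption due to AE, any duration (number of subjects, number of episodes, days held), with the subset of 7 days or more shown separately.* State whether the 7 days applies to one continuous episode.

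In SAP 6.1, add AEs leading to dose interruption to the summaries by consequence, alongside those for discontinuation, reduction and death.

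The cost is SAP wording and one or two extra tables, built on actions and dose changes that the protocol already requires to be recorded. The eCRF itself is not among the documents, so the sponsor should confirm that start and stop dates are captured for short holds. The reported interruption rate will look less favourable; keeping the 7-day subset preserves the planned figure beside it. No change to the management of subjects is implied.
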